## RELATIONSHIP BETWEEN FIBRINOGEN AND RISK OF ADVERSE COPD OUTCOMES

### Objectives

The primary purpose of this analysis is to assess the relationship between plasma fibrinogen concentration and adverse COPD clinical outcomes within varying time points that are relevant to a conduct of a clinical trial, and to support the Cox models described later. The association between fibrinogen levels and COPD exacerbations will be evaluated at time points of 12 months and 18 months. The association between fibrinogen levels and mortality will be evaluated at time points of 2 years and 3 years. The nature of the relationship will be critical to the determination of an appropriate cut-point or threshold defining “high” fibrinogen.

These analyses will:

- Define a cut-point for patients with high fibrinogen
- Describe and compare patients with high fibrinogen and patients with low fibrinogen according to demographic characteristics and covariates
- Assess the relation between high fibrinogen and the risk of COPD exacerbations within 12 and 18 months and mortality within 2 and 3 years
  - Identify predictors using recommended cut points
- Assess the time-to-event (COPD exacerbation and/or all-cause mortality) among patients with high fibrinogen
- Assess the impact of fibrinogen on the sample size of a hypothetical clinical trial

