### Proposed Analyses

1. Assess the time-varying relationship between high fibrinogen and the risk of adverse COPD outcomes.

*Analysis:*

Cox proportional hazards models will be used to identify hazard risk ratios with corresponding 95% confidence intervals associated with fibrinogen levels as well as demographic and clinical characteristics. These models will account for the time-varying nature of the relationship between fibrinogen levels and exacerbations/all-cause mortality; as such, they can only be performed in studies that recorded the dates of outcomes of interest. There will be two main groups considered in the modeling process:

1. Age 40+, GOLD stage 2+, history of exacerbations unspecified
2. Age 40+, GOLD stage 2+, and any prior COPD exacerbation (ECLIPSE)

Analyses using hospitalized exacerbations as an endpoint will be completed for outcomes which are recorded within 12 months of the initial fibrinogen measurement. Analyses with mortality will be completed for outcomes which are recorded within 3 years of the initial fibrinogen measurement. Analyses will be conducted using the fibrinogen thresholds determined previously (250 mg/dL, 300 mg/dL, 350 mg/dL, and 400 mg/dL).

Each outcome model will be constructed as follows:

1. The association between baseline characteristics and each outcome will be examined using univariate models. These models will be fitted on data of patients with high and low fibrinogen, and will result in a set of baseline characteristics that are predictive of the outcome and will be used as candidates for the final model.
2. To identify confounders of the cohort-outcome effect (e.g., the association between high vs. low fibrinogen and a given outcome), all baseline characteristics will be tested individually in a model with cohort as the only other independent variable. Those variables modifying the cohort-outcome effect size by at least 10% will create an additional set of candidates for the final model.
3. To obtain the fully adjusted model, the first step will be to add the candidate variables from step 2 to the unadjusted model one at a time, in descending order of strength of the confounder (i.e., the percentage change in the hazard ratio that results from adding that variable to the unadjusted model). Variables that still modify the cohort-outcome effect size by at least 10% will be retained, as will any that are significant predictors of the outcome at  $P < 0.05$ .

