4. The second step in constructing the fully adjusted model will be to take the model resulting from step 3, which will include all of the confounders and significant predictors forced into the model. Into that model, all of the significant predictor variables identified in step 1 that were not tested in step 3 will be entered and backward selection with  $P < 0.05$  used to select from among these additional variables. This will allow inclusion of significant predictors in the model that do not necessarily act as confounders.
5. Finally, a correlation matrix will be created for all variables included in the model in step 4. If two or more variables are found to be highly correlated with one another (i.e., a correlation of 0.90 or greater), the variable that acts as the stronger confounder or the stronger predictor of the outcome will be selected and the other variable dropped from the model.

Hazard ratios and 95% confidence intervals will be presented for each of the final outcome models.

*Variables for consideration:*

- Demographic and clinical characteristics

1. Assess the relation between high fibrinogen and the risk of adverse COPD outcomes over time.

*Analysis:*

Time-to-event analyses will be performed using survival analysis methods for patients with high fibrinogen in studies which recorded dates of hospitalized exacerbations (ARIC, CHS, and ECLIPSE) and all-cause mortality (ARIC, CHS, ECLIPSE, FHS, and NHANES). PROC PHREG will be used to create Kaplan Meier plots for each outcome, and plots will be repeated for each threshold assessed. Means, standard deviations, medians, and ranges of time-to-events will also be calculated.

*Variables for consideration:*

- Demographic and clinical characteristics
2. Assess the impact of using a fibrinogen threshold to select patients at higher risk of outcomes on the sample size of a hypothetical clinical trial

*Analysis:*

Survival estimates from the Cox models produced for each outcome will be used to generate power analyses to present the sample sizes of a hypothetical clinical trial designed to assess hospitalized exacerbations within 12 months or mortality within 36 months. Sample sizes will be presented for each fibrinogen threshold and will also be presented for hazard ratios of 0.6, 0.7, and 0.8. This analysis will assume a power of 0.8 and a 10% loss to follow-up. Equal sample sizes will be assumed for both “control” and “treatment” groups.

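### The Cox models are said to handle a time-varying fibrinogen effect but give one constant hazard ratio per window, omit two of four stated horizons, and are paired with curves for high-fibrinogen patients only

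*SAP*

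**What the plan says.** All references are to the SAP chapter Relationship between Fibrinogen and Risk of Adverse COPD Outcomes, unless stated.

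- **Horizons promised (Objectives).** "The association between fibrinogen levels and COPD exacerbations will be evaluated at time points of 12 months and 18 months". The same paragraph sets 2 and 3 years for mortality, and a bullet below it repeats all four.
- **Horizons modelled (Proposed Analyses, Cox item).** Hospitalized exacerbations are limited to 12 months after the first fibrinogen measurement. For death: "Analyses with mortality will be completed for outcomes which are recorded within 3 years of the initial fibrinogen measurement".
- **Claim about the model (same item).** "These models will account for the time-varying nature of the relationship between fibrinogen levels and exacerbations/all-cause mortality". The model is a proportional hazards model with fibrinogen split at 250, 300, 350 or 400 mg/dL. Fibrinogen Classification defines these as thresholds of baseline fibrinogen.
- **Time-to-event display (next item, headed as a relation over time).** "Time-to-event analyses will be performed using survival analysis methods for patients with high fibrinogen" in the studies with event dates. The Objectives carry the same restriction: "Assess the time-to-event (COPD exacerbation and/or all-cause mortality) among patients with high fibrinogen". On the plots: "PROC PHREG will be used to create Kaplan Meier plots for each outcome, and plots will be repeated for each threshold assessed".
- **Summaries in that item.** "Means, standard deviations, medians, and ranges of time-to-events will also be calculated".

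**The concern.** The Background section says the evidence gap is risk over a period that matters for running a trial. How the association behaves across such windows is therefore central to the qualification case. Three features of the plan work against showing it.

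1. A proportional hazards model with a fixed baseline covariate assumes that the HR is the same throughout the window. An association that is strong soon after the blood sample and then fades would be reported as one average.
2. The 18-month and 2-year results, which could show part of such a change, are promised and then not analysed.
3. The curves that a reader would use to see the time course have no low-fibrinogen comparator. The accompanying mean, SD and median times do not measure risk when most patients have no event.

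If the horizons are settled only after the data have been seen, the choice can also be criticised as data-driven.

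**Working it through.** The SAP gives no figure to reproduce here. The check is a comparison of sections plus illustrations.

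**1. Horizons side by side**

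| Outcome | Objectives | Cox item | Gap |
|---|---|---|---|
| Hospitalized exacerbation | 12 and 18 months | 12 months | months 12-18 lie wholly outside the window |
| Death | 2 and 3 years | 3 years | 2 years lies inside the window, but no 2-year HR is planned |

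No other section restores them. The histograms stratified by outcome and the sample-size item use 12 and 36 months, and the logistic model in Assessment of Key Assumptions names no horizon.

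**2. Claim against specification.** The Cox item contains five model-building steps. None has a fibrinogen-by-time term, a piecewise HR or a proportionality check. General Statistical Considerations speaks of pooling so as to uphold model assumptions but names no check. Updating fibrinogen during follow-up is not specified either, and the SAP's section on longitudinal variation describes ECLIPSE as the only study with repeated measurements.

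**3. What one HR per window can hide.** Assumptions: constant low-group hazard, few events, little early censoring, half of patients high. Then approximately

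HR over window H ≈ Σ(HR in period k × months of period k inside H) / H.

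- Yearly HRs 2.0, 1.5, 1.0: 18 months (2.0×12 + 1.5×6)/18 = 1.83; 24 months (24 + 18)/24 = 1.75; 36 months (24 + 18 + 12)/36 = 1.50.
- Yearly HRs 2.0, 1.0, 1.0: 18 months (24 + 6)/18 = 1.67; 24 months 36/24 = 1.50; 36 months 48/36 = 1.33.

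A Cox fit to 400,000 simulated patients, with 36-month death risk set near the Table 1 crude value of 585/6,376 = 9.2%, agrees:

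| Assumed yearly HRs | 12 m | 18 m | 24 m | 36 m |
|---|---|---|---|---|
| 2.0, 1.5, 1.0 | 2.02 | 1.85 | 1.77 | 1.51 |
| 2.0, 1.0, 1.0 | 2.02 | 1.69 | 1.52 | 1.34 |
| 1.5, 1.5, 1.5 | 1.55 | 1.54 | 1.52 | 1.51 |

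The first and third rows give the same 36-month HR. Only shorter windows or a time term tell them apart.

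**4. Could the pooled data detect this?** Under 2.0, 1.5, 1.0 with equal groups, the yearly average hazards stand as 1.5 : 1.25 : 1.0. The 585 deaths then split as about 234, 195 and 156.

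- Year 1: 156 high and 78 low deaths; variance of log HR = 1/156 + 1/78 = 0.0192.
- Year 3: 78 and 78 deaths; variance = 2/78 = 0.0256.
- SE of the difference = √0.0449 = 0.21, against ln(2.0/1.0) = 0.69, about 3.3 standard errors.

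So a pooled check is worthwhile for a change of this size. It would be weaker at a threshold that splits patients unevenly, and uninformative in a single small study (Framingham has 13 deaths).

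**5. Event-time summaries.** Crude proportions from Table 1, taking the counts as patients and the COPD column as denominator:

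- Exacerbation within 12 months: ARIC 96/1,789 = 5.4%; CHS 236/1,292 = 18.3%; ECLIPSE 335/2,118 = 15.8%.
- Death within 3 years: ARIC 86/1,789 = 4.8%; CHS 120/1,292 = 9.3%; ECLIPSE 220/2,118 = 10.4%; Framingham 13/145 = 9.0%; NHANES III 146/1,032 = 14.1%.

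All are far below 50%, so no whole-study median is reached in these windows. A mean taken over patients with events describes timing, not risk. A mean that includes censored times mainly reflects length of follow-up.

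**The case against.** - **The contrast exists.** A reader might infer that the plan cannot compare high with low fibrinogen. It can: the Cox item fits models on both groups, treats high versus low as the effect of interest, and presents HRs with 95% confidence intervals. This objection stands. Only the display lacks a comparator.
- **The display matches its objective.** The Objectives bullet is itself limited to high-fibrinogen patients, so the restriction is not a slip. That is so, but it does not fit the item's own heading, which announces a relation.
- **Naming a Cox procedure for Kaplan-Meier plots.** A reader might infer that the curves are forced to be proportional. That would need fibrinogen as a covariate, which the item does not state and which could not vary in a high-only sample. Without covariates (300 events in 2,000 patients), the Cox-type curve ends at 0.85004 against 0.85000 for Kaplan-Meier. The choice of procedure is harmless.
- **Loose wording.** The sentence on time variation goes on to say that the models need studies with event dates, so it may mean no more than time-to-event. That is plausible, but the statement and the item's heading would still be inaccurate and no proportionality check is planned.
- **Fixed-window purpose.** For a trial of the same length as the window, an average HR is interpretable. With few events and little early censoring it is close to the ratio of cumulative hazards at the end of the window. This stands and limits the harm to the 12- and 36-month sample sizes. It does not help shorter trials: in the fading example the ratio is 2.0 at 12 months and 1.75 at 24, not 1.5.
- **Size of the spread in Table 1.** A reader might take the range of event proportions as the effect at stake. It is a difference between studies, not between fibrinogen groups.

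**Conclusion.** The concern holds in this limited form and should be fixed before analysis; it does not invalidate the main comparison. Two points rest on the text alone: the Objectives and the Cox item disagree on horizons, and a constant-HR model is described as accounting for time variation. A third is that the time-to-event display, headed as a relation, names no low-fibrinogen curve.

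The size is illustrative. Under the assumed fading pattern, the planned 36-month HR (1.51) equals that of a constant effect, while the unplanned 24-month HR differs (1.77 against 1.52). The yearly HRs and the equal split are assumptions; the SAP gives neither. Whether fibrinogen's effect really fades cannot be judged from the document.

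The remark on medians assumes that the 12-month and 3-year windows apply to the display, which sets none of its own. Over the longer follow-up of some cohorts a median might be reached, but outside the period of interest. Table 1 is not split by fibrinogen, so a high-fibrinogen subgroup could have higher risk; half its patients would need an event for the median to be reached. The point about means and medians is minor.

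**What to change.** 1. **Horizons.** Run the Cox models at 12 and 18 months for exacerbations and at 2 and 3 years for death. Otherwise, remove 18 months and 2 years from the Objectives with a reason, so that the two sections agree.
2. **Time variation.** Add a fibrinogen-by-time term or piecewise HRs (for example 0-12 and 12-18 months; 0-2 and 2-3 years) as the proportionality check, and say what will be reported if proportionality fails. Reword the statement that the models account for a time-varying relation.
3. **Curves.** Plot Kaplan-Meier curves for high and low groups as strata at each threshold. A log-rank test stratified by study can accompany the pooled plots. Align the Objectives bullet.
4. **Summaries.** Replace mean, SD and median event times with cumulative incidence and 95% confidence intervals in both groups at each horizon.

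The cost is SAP wording and standard SAS output on the integrated database. No new data collection is proposed. If 18-month exacerbation follow-up proves incomplete in a study, the report should say so.
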